3.0 Inclusion and Exclusion Criteria

3.1 Describe the criteria that define who will be included or excluded in your final study sample.

Respons Inclusion Criteria:

•Male and female participants aged 18 years or older

•Diagnosed with unilateral definite Ménière's disease according to the AAO-HNS 1995 criteria, confirmed by an ENT

•Active vertigo: at least two Ménière's vertigo attacks (defined as lasting 20 minutes or longer and associated with tinnitus, ear fullness, or low frequency hearing loss and nausea/vomiting) every four weeks during the eight-week qualification period and at least two or more Ménière's vertigo attacks during the lead-in phase prior to randomization

•Documented unilateral lower frequency hearing loss defined as the fourtone average (arithmetic mean rounded to the nearest whole number) of the pure-tone thresholds at 0.25, 0.5, 1 and 2 kHz more than or equal to 25 dB of the worse audiogram during the six months before screening

•Have tried diuretics for at least one month and discontinued treatment due to continued vertigo attacks

•All other co-existing medical or psychiatric conditions are stable, and no greater than moderate severity

•Willing to avoid pregnancy during the entirety of the study (abstinence or two forms of acceptable birth control, such as condoms and oral contraceptives)

Exclusion Criteria:

•Bilateral Ménière's disease

•Current or past history of migraine

•Any other neuro-otologic disease or major vestibular abnormality found during screening that could confound the evaluation of Ménière's symptoms

•Previous intolerance or sensitivity to lamotrigine

•On any prohibited medication within four weeks prior to the study

•History of tympanostomy tubes with evidence of perforation or lack of closure

•IT gentamicin injections or endolymphatic sac surgery within the last year

•History of or current immunodeficiency disease, nephrolithiasis, hypertension, cardiac disease, arrhythmia, hypercholesterolemia, hemiplegic/basilar migraine, stroke, diabetes, vascular disease or kidney disease

•Family history of unexplained deafness

•Pregnant or breastfeeding

•Current diseases or conditions that may be associated with an altered perception of processing stimuli

•Current severe medical condition(s) that in the view of the investigator prohibits participation

•Previously used the investigational drug

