•Current non-vertiginous dizziness (orthostatic or panic disorder) unless it could be clearly differentiated from Ménière's attacks by the participante:

3.2 Describe how individuals will be screened for eligibility.

Response:

[name] conducts and orders a physical exam and relevant testing to assure subjects meet criteria outlined.

Participants who are diagnosed with Ménière's disease, as determined by clinical history, ENT confirmation and an audiogram, will qualify if they also have had two or more Ménière's vertigo attacks in a four-week span for two consecutive four-week periods (the qualification period). Those who meet these criteria will then need two or more Ménière's vertigo attacks during a four-week lead-in period to further establish a baseline and verify randomization eligibility. Participants are allowed from the beginning of the lead-in to take their choice of a symptomatic abortive medication according to its package instructions for Ménière's vertigo attacks that last longer than 30 minutes with nausea and/or vomiting. Symptomatic abortive medications include, but are not limited to, meclizine (Antivert), Valium, diazepam, or Zofran.

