A total of 25 participants will be enrolled for the pre-randomization stage. Those who do not wish to continue to the next stage or who no longer meet inclusion/exclusion criteria will be replaced. At screening, participants will be asked to undergo a urine pregnancy for women of reproductive age (<50yrs) to ensure that they are eligible to continue. If a complete blood count (CBC), comprehensive metabolic profile (CMP), and creatinine clearance has not been conducted within the past three months, the participant will have blood drawn into tubes that will be centrifuged and shipped to Kaleida Health's labs to be analyzed. A urine sample will be obtained for the 24 hour creatinine clearance analysis as a screening measure for healthy kidney and liver function. As part of the patient's routine medical care, the blinded PI will conduct a full neurological and physical exam, review prior and current medications and request all medical history of the participant's Ménière's disease. This includes any results from vestibular testing that confirm the Ménière's diagnosis and rule out other causes (e.g. a basic vestibular exam, four calorics, rotary chair, and posturography testing). If participants have not undergone a comprehensive audiogram (including electrocochleaography and tympanometry subtests) and an electrocardiogram within the past three months, they will undergo all of the missing tests at the Dent Neurologic Institute before enrollment. These tests are test for other disorders that may require treatment as part of the patient's standard medical care and to also function to verify eligibility and establish a baseline for improvement and possible adverse events during the study. Participants will be asked to complete a series of questionnaires that include the Dizziness Handicap Inventory (DHI). Ménière's Disease Patients-Oriented Severity Index (MDPOSI), Ménière's disease Self-Assessment, Tinnitus Handicap Inventory (THI), Patient Health Questionnaire (PHQ-9), Generalized Anxiety Disorder (GAD-7) and the baseline Columbia-Suicide Severity Rating Scale (C-SSRS). These assessments will provide a baseline of the participant's symptom severity, frequency and duration of vertigo attacks and quality of life.

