Following the screening visit, participants will enter a four week lead-in period. They are responsible for recording vertigo and other symptom severity, and abortive medication use with the Ménière's daily survey. During this period any uncompleted audiogram or EKG testing can take place. This lead-in period will provide a more accurate representation of the Ménière's disease vertigo frequency and allow for screening tests to be completed at the participant's convenience. If the participant is on any prohibited medication at the screening, the medications will be discontinued if the participant wishes to continue in the study and it is deemed safe by the PI and the prescribing doctor. The lead-in period will also be used as a wash-out.

At Visit 2, after the four week lead-in, inclusion/exclusion criteria will be re-evaluated. This includes a review of any concomitant

medications. Participants will be asked to hand in their Ménière's survey if they opted for the paper document. The surveys will be reviewed to ensure that abortive measures were only used during the severe attacks, as instructed. The Principal Investigator will assess any possible adverse events and then staff will administer the questionnaire batch. If the participant is eligible for randomization, he/she will be assigned to either a placebo or lamotrigine treatment group. Assignment will be based on a randomization conducted by UBSoPPS Research pharmacists, and the participant will be considered "enrolled" in the study at this point, and from this point on, all medical services, except abortive medication(s) of the patient's choice) are study-related and are not billed to the patient's insurance.

- 3.3 Indicate specifically whether you will include or exclude each of the following special populations: (You may not include members of these populations as subjects in your research unless you indicate this in your inclusion criteria.)
 - *Adults unable to consent*
 - Individuals who are not yet adults (infants, children, teenagers)
 - Pregnant women
 - Prisoners

Response:

Exclude all

3.4 Indicate whether you will include non-English speaking individuals. Provide justification if you will exclude non-English speaking individuals.

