At Visit 2, after the four week lead-in, inclusion/exclusion criteria will be re-evaluated. This includes a review of any concomitant medications. Participants will be asked to hand in their Ménière's survey if they opted for the paper document. The surveys will be reviewed to ensure that abortive measures were only used during the severe attacks, as instructed. The Principal Investigator will assess any possible adverse events and then staff will administer the questionnaire batch. If the participant is eligible for randomization, he/she will be assigned to either a placebo or lamotrigine treatment group. Assignment will be based on a randomization conducted by UBSoPPS Research pharmacists, and the participant will be considered "enrolled" in the study at this point, and from this point on, all medical services, except abortive medication(s) of the patient's choice) are study-related and are not billed to the patient's insurance. Both groups will receive an amber vial of 28 pills with instructions to take one pill twice a day. Those in the lamotrigine group will be taking 25mg BID while those in the placebo group will be taking encapsulated microcrystalline cellulose. A drug dosage log will also be given to participants and they will be asked to write down the number of pills taken. Participants will be advised to notify the Principal Investigator or study staff if they develop rashes or other side effects. If the principal investigator decides that the rash is medication related, the participant will immediately stop the medication, return for an early termination visit and be terminated early from the study. Serious adverse events requiring withdrawal and unrelated to rash will return for an early termination visit and begin a two-week taper. If at any visit a participant is found to be non-compliant with dosing instructions, the Principal Investigator will assess the situation and determine if early termination is required. If the participant is terminated, they will follow the same taper schedule and early termination visit required for those withdrawing due to adverse events other than rash. Staff members will also remind participants to complete the daily survey and how to do so.

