At Visit 5, current medications and adverse events will be reviewed by the Principal Investigator. Participants will complete another physical and neurological exam, a comprehensive audiogram with tympanometry, and a urine pregnancy test for females of reproductive age (<50yrs). Blood will be drawn, centrifuged and shipped to Kaleida Health's labs to analyze study drug levels. Additionally, a urine sample will be obtained for 24 hour creatinine clearance analysis as a screening measure for healthy kidney and liver function, to verify participants' ability to continue in the study. Study drug level results will be separated from other testing results and sent to UBSoPP Research Pharmacy to hold until the blind is broken and compliance can be reviewed. A staff member will collect the medication containers, conduct a pill count and collect and review the dosage log and daily Ménière's survey responses. If the participant is determined to be compliant, the staff member will administer the questionnaire batch. Continuing participants will receive an amber vial of 56 pills with instructions to take one pill twice a day. Participants' clinical response and tolerability will be assessed and if a participant reports no serious side effects from medications, the study drug will be further titrated to 150 mg BID or the matching placebo. If the participant finds that they cannot tolerate the 150mg BID dose, they are able to come into the clinic for an unscheduled visit and decrease to 100mg BID. Staff members will then hand out another dosage log and remind participants to complete the daily survey. Participants are asked to return in four weeks.

At Visit 6, current medications and adverse events will be reviewed by the Principal Investigator. A staff member will collect medication containers, conduct a pill count and collect and review the dosage log and daily Ménière's survey responses. If the participant is determined to be compliant the staff member will administer the questionnaire batch. Continuing participants will receive an amber vial of 56 pills of the same dosage, either 150mg BID or 100mg BID, with instructions to take one pill twice a day. Staff members will then hand out another dosage log and remind participants to complete the daily survey. Participants are asked to return in four weeks.

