Four weeks later participants return to the clinic for Visit 8, current medications and adverse events will be reviewed by the Principal Investigator. The Principal Investigator will also administer a neurological and physical exam and complete the Clinical Global Impression-Severity and Change assessment. A staff member will collect medication containers, conduct a pill count and collect and review the dosage log and daily Ménière's survey responses. Participants will complete the questionnaire batch, and undergo a comprehensive audiogram with tympanometry. Blood will be drawn, centrifuged and shipped to Kaleida Health's labs to analyze study drug levels, CMP, CBC, and a urine pregnancy test will be conducted for female participants of reproductive age (<50yrs). Additionally, a urine sample will be obtained for 24 hour creatinine clearance analysis as a screening measure for healthy kidney and liver function. At the conclusion of the visit a staff member will be un-blinded by unsealing an envelope that contains treatment code and participant number. Those in the lamotrigine group will be given the option to be terminated from the study, but to continue the study medication at their own cost. Alternatively, they can continue in the study and begin to taper off the study drug. Those who decide to continue the study medication will be noted, but no further study participation is required. Participants continuing lamotrigine will be free to follow up on their treatment through the Dizziness and Balance Clinic or through a physician of their choice. Participants who decide to discontinue the study drug will begin a two-week taper consisting of one week at their current dosage QD and then one week of half the current dosage QD, and be paid for these 2 remaining study visits 9 and 10. Those assigned to the placebo group will be terminated from the study and are informed that they are allowed to seek treatment for their Ménière's disease at the Dizziness and Balance Clinic or elsewhere.

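### No pregnancy test is scheduled at Visit 2, when dosing starts: the last one is four weeks earlier and the next is six weeks into treatment

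*Combined protocol and SAP*

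**What the plan says.** Pregnancy and breastfeeding are exclusions in Section 3.1. Section 14.3 gives fetal safety as the reason and describes lamotrigine as a Category C drug. Section 3.1 also requires participants to be "Willing to avoid pregnancy during the entirety of the study (abstinence or two forms of acceptable birth control, such as condoms and oral contraceptives".

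The visit descriptions name a urine pregnancy test at three points:

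- Screening (Section 3.2): participants "undergo a urine pregnancy for women of reproductive age (<50yrs) to ensure that they are eligible to continue".
- Visit 5 (Section 9.2): "a urine pregnancy test for females of reproductive age (<50yrs".
- Visit 8 (Section 9.2): "a urine pregnancy test will be conducted for female participants of reproductive age (<50yrs".

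Treatment starts at Visit 2. Section 9.2 states: "At Visit 2, after the four week lead-in, inclusion/exclusion criteria will be re-evaluated". Eligible participants are then randomised, and "Both groups will receive an amber vial of 28 pills with instructions to take one pill twice a day". The Visit 2 text appears in both 3.2 and 9.2. It lists a concomitant medication review, a survey review, an adverse event assessment and the questionnaires, but no pregnancy test. Visits 3 and 4 list none either.

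**The concern.** Pregnancy status can change during a four-week lead-in. The plan treats it as important enough to test at screening, after titration and at the end of treatment, but not at the moment when exposure begins. Other changeable items are checked again at Visit 2: concomitant medication, the lead-in attack count and, under Section 14.1, suicidality.

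A woman with an unrecognised pregnancy from around screening or the lead-in could be randomised to lamotrigine and taken through three dose levels before any scheduled test could detect it. Symptoms are a poor substitute for a test in this trial. Nausea or vomiting is part of the attack definition in Section 3.1, and nausea, vomiting and dizziness are among the lamotrigine risks in Section 14.1. Early signs of pregnancy could be put down to the disease or the drug.

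This is a matter of participant safety. Sample size, power and type I error are not affected.

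**Working it through.** **Timing.** Inputs are the phase lengths in Section 7.1 (lead-in 4 weeks, titration 6 weeks, study period 12 weeks) and the visit spacing in Section 9.2.

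- Screening to Visit 2: 4 weeks.
- Visit 2 to Visit 5: 2 + 2 + 2 = 6 weeks. The dispensing agrees: three vials of 28 pills at 2 per day is 3 × 14 = 42 days. This matches the titration length in the plan.
- Visit 5 to Visit 8: 4 + 4 + 4 = 12 weeks.

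| Schedule | Test weeks relative to first dispensing | Last test to first dose | First dose to next test |
|---|---|---|---|
| As written | −4, +6, +18 | 4 weeks | 6 weeks |
| With a Visit 2 test | −4, 0, +6, +18 | 0 weeks | 6 weeks |

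As written, the interval between tests that spans the start of treatment is 4 + 6 = 10 weeks. Section 12.4 describes a visit frequency that does not fit a lead-in without visits, but it adds no pregnancy test.

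**Exposure before the Visit 5 test.** Section 9.2 gives 25, 50 and 100 mg twice daily for 14 days each:

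14 × 50 + 14 × 100 + 14 × 200 = 700 + 1,400 + 2,800 = 4,900 mg.

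**Expected number of events.** The plan does not say how many randomised participants are women under 50. The update in Section 11.2 asks for a total of 16 with equal groups, so the count lies between 0 and 16. Assume a conception risk of 0.001 to 0.01 per woman over the four weeks with the required contraception. This is an assumption and is not in the documents.

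- Lower end, 1 woman: 1 × 0.001 = 0.001; halved for allocation, 0.0005 on lamotrigine.
- Upper end, 16 women: 16 × 0.01 = 0.16; halved, 0.08 on lamotrigine.

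**Participants still to reach Visit 2.** The same update (June 2015) reports 8 completed and 2 dropped out. If all ten had passed Visit 2, at most 16 − 8 − 2 = 6 could benefit from a change. Then 6 × 0.01 = 0.06 is the most that could be expected, with 0.03 on lamotrigine.

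**The case against.** The strongest reply is that pregnancy does not go unassessed at Visit 2. Section 3.2 opens by giving the investigator the task of ordering whatever testing is needed to confirm the criteria. All criteria, including pregnancy, are re-evaluated before randomisation. Abstinence or two contraceptive methods are required, and adverse events are reviewed every two weeks during titration. On this view the plan only fails to name a method. The reply softens the point but does not answer it. None of these provisions schedules an objective test, and contraception and symptom questions rest on adherence and self-report. The plan's own tests at Visits 5 and 8 show that it does not rely on contraception alone.

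Other points stand in part:

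- The supplied text has no schedule-of-events table and the consent pages are not available, so the absence is read from the narrative. Section 25.2 mentions urine containers for Visits 1, 5 and 8 only. These are probably for the creatinine collection, so they add little.
- Section 3.2 lets screening tests be finished during the lead-in, so some pregnancy tests may fall later than four weeks before dosing. The text does, however, place this test at screening.
- The upper figure of 0.16 supposes that every participant is a woman under 50. The trial enrols both sexes with no upper age limit and plans to advertise in a newspaper for people over 50, so the true figure is very likely well below this.
- The documents link no cumulative dose to fetal risk. The 4,900 mg describes exposure and is not a measure of harm.
- A Visit 2 test could miss a very early conception, so fewer pregnancies are preventable than the range suggests.

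**Conclusion.** The concern holds. Followed as written, the plan starts a drug it calls Category C on a pregnancy result that is four weeks old, and schedules no further test until six weeks into dosing. The two intervals come directly from the plan. The expected-event range depends on the assumed conception risk and on an unknown number of women under 50, and it shows that the event is unlikely. The plan should be changed because the harm is serious and avoidable and the remedy is a test the trial already performs.

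**What to change.** Keep the screening test: it comes before the medication washout ("The lead-in period will also be used as a wash-out") and before the drugs permitted during the lead-in ("Participants are allowed from the beginning of the lead-in to take their choice of a symptomatic abortive medication"). Add the same urine pregnancy test at Visit 2 for women under 50, once the other criteria are confirmed, with a negative result required before randomisation and before the first vial is dispensed. Testing before randomisation also avoids randomising someone who must then be withdrawn, which matters in a trial of 12 to 16.

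The cost is one line in each Visit 2 description (Sections 3.2 and 9.2) and one extra test per woman under 50 at a visit that already takes place. That is at most 16 tests, or at most 6 if the ten participants in the June 2015 update had already passed Visit 2. The 6-week gap to Visit 5 and the 12-week gap to Visit 8 remain, so the contraception requirement and both later tests must stay.

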4.0 Study-Wide Number of Subjects (Multisite/Multicenter Only)

4.1 If this is a multicenter study, indicate the total number of subjects to be accrued across all sites.

Response:

N/A – not a multicenter study

5.0 Study-Wide Recruitment Methods (Multisite/Multicenter Only)

If this is a multicenter study and subjects will be recruited by methods not under the control of the local site (e.g., call centers, national advertisements) describe those methods. Local recruitment methods are described later in the protocol.

5.1 Describe when, where, and how potential subjects will be recruited.

Response:

N/A - not a multicenter study

5.2 Describe the methods that will be used to identify potential subjects.

Response:

N/A – not a multicenter study

5.3 Describe materials that will be used to recruit subjects. (Attach copies of these documents with the application. For advertisements, attach the final copy of printed advertisements. When advertisements are taped for broadcast, attach the final audio/video tape. You may submit the wording of the advertisement prior to taping to preclude re-taping because of inappropriate wording, provided the IRB reviews the final audio/video tape.)

Response:

The study hopes to recruit from the patient population at the Dent Dizziness and Balance Center and Buffalo ENT Specialists, LLP. In doing so, the PI and staff will have to access medical charts/records to verify eligibility and diagnosis of Meniere's disease prior to obtaining consent of potential participants. A referral letter will also be sent to area physicians and ENT specialists informing them of the study design and inclusion/exclusion criteria. Those receiving the letter are encouraged to notify eligible patients of the opportunity to participate and how to contact the study staff if they are interested. If enrollment numbers are not met, another letter will be sent out to remind the physicians and specialists. If enrollment numbers are still not met through this method, recruitment strategies will include an advertisement in the once monthly issue of an After 50 free newspaper, Buffalo Healthy Living magazine, 32 sixtysecond radio advertisements and 50 sixty-second streaming commercials for two weeks. The study has requested funds for this purpose, but is hoping to exhaust all other potential participants within the Dizziness and

Balance Center and Buffalo ENT Specialists first. Therefore, the additional newspaper and radio advertisement recruitment materials will be submitted as an addendum at a later date.

